12.5.1 Control of Familywise type I error rate

The null hypothesis to be rejected for the relevant secondary endpoints are:

- H_{02} : The mean relative changes from baseline in LDL-C level, averaged over all post baseline visits during the double-blind treatment period, are equal between treatment groups.
- H_{03} : The odds regarding participants experiencing at least one muscle-related AE as defined in the SMQ rhabdomyolysis / myopathy from day 1 to day 360 are equal between treatment groups.
- H_{04} : The annualized mean number of days pain is experienced is equal between both groups.
- H_{05} : The mean change from baseline in SF-BPI pain severity score from day 1 to day 360 is equal between treatment groups.
- H_{06} : The mean change from baseline in SF-BPI pain interference score from day 1 to day 360 is equal between treatment groups.

[figure not shown]
Hypotheses are grouped into three families. The first family contains the primary hypothesis H_{01} . The second family contains two secondary hypotheses H_{02} and H_{03} . The third family contains the rest of secondary hypotheses H_{04} , H_{05} and H_{06} . The hierarchical testing strategy is applied to these three families. First H_{01} is tested at level alpha. If it is rejected, we test the second family using a closed test at level alpha. If both H_{02} and H_{03} are rejected, we test the third family using the Hommel procedure at level alpha. When not all hypotheses in a family can be rejected, testing stops at the corresponding family and does not proceed to test the next family.

Within the second family, a closed test procedure based on weighted Simes tests is applied with 80% weight for H_{02} and 20% weight for H_{03} . First the two nominal p-values for H_{02} and H_{03} are simultaneously compared to alpha. If both nominal p-values are \leq alpha, the two null hypotheses are rejected. Otherwise compare the individual nominal p-values to the weighted alpha with the pre-specified weights (0.8/0.2) separately. If the p-value for H_{02} is $\leq 0.8 \cdot \alpha$, H_{02} is rejected; If the p-value for $H_{03} \leq 0.2 \cdot \alpha$, H_{03} is rejected.

Within the third family, the Hommel procedure is applied. Let the ordered p-values for H_{04} , H_{05} , H_{06} be $p(1) \leq p(2) \leq p(3)$ and the corresponding hypotheses $H(1)$, $H(2)$ and $H(3)$. First if $p(3) \leq \alpha$, we can reject all three hypotheses. Otherwise, if $p(2) \leq \alpha / 2$, reject $H(2)$ and $H(1)$. Otherwise, if $p(1) \leq \alpha / 3$ or ($p(1) \leq \alpha / 2$ and $p(2) \leq 2\alpha / 3$), reject $H(1)$.

This testing procedure controls the familywise error rate at level alpha in the strong sense. [Figure 12-1](#) below shows the applied testing procedure.

Figure 12-1 Applied testing procedure

12.5.2 Efficacy endpoints

For muscle-related AE / SMQ rhabdomyolysis / myopathy the SAF will be used for analysis. For all other secondary efficacy analyses the Full Analysis Set (FAS) will be used.

12.5.2.1 Relative change (percentage) from baseline to mean LDL-C level over the double-blind treatment period

The relative change (percentage change) from baseline in LDL-C level averaged over the double-blind treatment period will be analyzed using a mixed model for repeated measures (MMRM) including treatment group, stratification factor (cardiovascular risk category: very high risk, high risk), scheduled visit and the interaction of treatment group with scheduled visit as factors and baseline LDL-C level and the interaction of baseline LDL-C level with scheduled visit as covariates. Visit will be included as a categorical variable, and an unstructured covariance matrix will be used for the model. The null hypothesis of equal mean changes between both groups to the average over all post baseline visits will be tested by an appropriate linear contrast of the variable treatment and treatment by visit interaction. The null hypothesis will be rejected within the confirmatory testing framework, if the 1-sided p-value is <0.025 . The adjusted mean change from baseline and its corresponding 95% confidence interval will be presented.

For this endpoint a graphical presentation of the course of the regarding variable over time will be shown additionally to the analysis. Further details for this graphical presentation and for the analysis of secondary endpoints will be provided in the statistical analysis plan (SAP).

12.5.2.2 Muscle-related AE / SMQ rhabdomyolysis / myopathy

The proportion of participants experiencing at least one muscle-related AE as defined in the SMQ rhabdomyolysis / myopathy from day 1 to day 360 will be analyzed in a logistic regression model. Treatment and determined LDL-C target at screening will be included as factors in the model. The LDL-C targets depend on the participants' CV risk category and will be attributed directly from the CV risk category eCRF entries. Therefore, the CV risk category will be included in the model as the stratification factor ("very high risk", "high risk"). The odds ratio and its 95% confidence interval (CI) and p-value will be estimated. The null hypothesis of equal odds will be rejected within the confirmatory testing framework if the 1-sided p-value from the logistic regression model for the factor "treatment" is <0.025 .

Additionally, the relative risk as well as absolute risk difference and their 95% confidence intervals will be estimated from a Cochran-Mantel-Haenszel test (CMH) stratified for the determined LDL-C target before randomization based on the Score statistic.

In case of missing values muscle-related AE / SMQ rhabdomyolysis / myopathy will not be imputed but analyzed according to last known status of the occurrence of an event. To investigate the sensitivity to missing values or potentially different observation times in the two study arms, a time to the first experience of at least one muscle-related AE as defined in the SMQ rhabdomyolysis / myopathy will be conducted.

12.5.2.3 Number of days participants experiencing self-reported pain from day 1 to day 360

The number of pain days experienced will be analyzed using a negative binomial model (P. McCullagh and J.A. 1989) with the number of observed pain days as the dependent variable and treatment group and stratification factor (cardiovascular risk category: very high risk, high risk) as fixed-effect factors and log (follow-up duration in years) as the off-set. The annualized incidence rates and their 95% confidence intervals estimated from the model will be provided by treatment group. The treatment comparison will be performed through the estimated incidence rates. The incidence rate ratio and its 95% confidence interval will be provided.

12.5.2.4 Mean change from baseline in SF-BPI pain severity score and pain interference score at day 360

Mean change from baseline in SF-BPI pain severity score and SF-BPI pain interference score at day 360 will be analyzed using a mixed model for repeated measures (MMRM). Treatment group, stratification factor (cardiovascular risk category: very high risk, high risk), scheduled visit, and the interaction of treatment group with scheduled visit will be included as fixed factors in model, baseline SF-BPI value and the interaction of baseline SF-BPI value with scheduled visit will be included as a fixed covariate. Beyond that visit will be included as a repeated factor nested within participant and an unstructured covariance matrix will be used for the model.

The adjusted mean change from baseline at day 360 and its regarding 95% confidence interval will be presented. The null hypothesis of equal mean changes will be rejected based on the treatment contrast at regarding visits according to a 1-sided p-value <0.025 within the confirmatory testing framework.

For this endpoint a graphical presentation of the course of the regarding variable over time will be shown additionally to the analysis. Further details for the analysis and the graphical presentation will be provided in the statistical analysis plan (SAP).

12.5.3 Safety endpoints

The Safety Set (SAF) will be used for safety analyses, including the secondary safety endpoint.

For all safety analyses, the safety set will be used. All listings and tables will be presented by treatment group. Safety summaries (tables, figures) include all data from the double-blind treatment period and baseline data. In particular, summary tables for AEs will summarize all events obtained during double-blind treatment period, with a start date during the double-blind treatment period. Additionally, all summary tables for AEs will be repeated for on-treatment AEs only (TEAEs). A separate summary for death will be provided.

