The "X" in the table denotes the assessments to be recorded in the clinical database or received electronically from a vendor. The "S" in the table denotes the assessments that are only in the participant's source documentation and do not need to be recorded in the clinical database.

PRO measure(s) are strongly recommended to be completed before any clinical assessments are performed at any given visit (with the exception of the pain diary which should be completed as described in [Section 8.5.1.2](#)).

Participants will have to comply with the following restrictions during the study:

- Fasted for all visits with LDL-C assessment and assessment of other lipid samples.
- Must refrain from unaccustomed strenuous physical exercise for 48 hours before the screening and any study visit until the double-blind treatment period has been completed.

As per [Section 4.6](#), during a Public Health emergency as declared by Local or Regional authorities i.e. pandemic, epidemic or natural disaster that limits or prevents on-site study visits, alternative methods of providing continuing care may be implemented by the investigator as the situation dictates. If allowable by a local Health Authority and depending on operational capabilities, phone calls, virtual contacts (e.g. tele consult) or visits by site staff/ home nursing staff to the participant's home, can replace on-site study visits, for the duration of the disruption until it is safe for the participant to visit the site again.

Table 8-1 Assessment Schedule

Period	Screening	Run-In				Baseline		Treatment										Follow-up call	
Visit Name	Screening ¹	Run-In Period ²				Baseline ³		Treatment								Prior to PCSK9mAb switch ⁵	Unscheduled	EOT/EOS ²²	Follow-up call +30 days
Days	-144 to -130	-130	-100	-70	-40	-10	1	30	60	90	120 ⁴	150	210	270	330	UNS	UNS	360	390
Informed consent	X																		
Inclusion / Exclusion criteria	X						X												
Demography	X																		
Medical history/current medical conditions	X																		
CV Disease, Alcohol and COVID-19 Vaccination History	X																		
Smoking status	X	X	X	X	X		X	X	X	X	X ⁴	X	X	X	X				
(Other) prior/concomitant medications	X	X	X	X	X		X	X	X	X	X ⁴	X	X	X	X		X	X	
Prior/Concomitant lipid lowering therapies (types and doses)	X	X	X	X	X		X	X	X	X	X ⁴	X	X	X	X		X	X	
Surgical/medical procedures ⁶		X	X	X	X		X	X	X	X	X ⁴	X	X	X	X		X	X	
Lifestyle instructions	X	X	X	X	X		X	X	X	X	X ⁴	X	X	X	X		X	X	

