10.1.3 SAE reporting

To ensure participant safety, every SAE, regardless of causality, occurring after the participant has provided informed consent and until 30 days after the last study visit must be reported to Novartis safety immediately, without undue delay, but under no circumstances later than within 24 hours of obtaining knowledge of the events (Note: If more stringent, local regulations regarding reporting timelines prevail). Detailed instructions regarding the submission process and requirements are to be found in the investigator folder provided to each site. Information about all SAEs occurring before EOS visit is collected and recorded on the eSAE page with paper backup and as paper during the 30 days safety follow-up period after EOS; all applicable sections of the form must be completed in order to provide a clinically thorough report.

SAE reporting time frames are as follows:

1. SAEs occurring after the participant has provided informed consent until the time the participant is deemed a Screen Failure must be reported to Novartis.

2. SAEs occurring between time participant signs ICF until time that participant is determined to be a run-in failure must be reported to Novartis.
3. SAEs occurring between time participant signs ICF until 30 days after EOS must be reported to Novartis.

All follow-up information for the SAE including information on complications, progression of the initial SAE and recurrent episodes must be reported as follow-up to the original episode immediately, without undue delay, but under no circumstances later than within 24 hours of the investigator receiving the follow-up information (Note: If more stringent, local regulations regarding reporting timelines prevail). An SAE occurring at a different time interval or otherwise considered completely unrelated to a previously reported one must be reported separately as a new event.

If the SAE is not previously documented in the Investigator's Brochure or Package Insert (new occurrence) and is thought to be related to the study treatment, a PV & PS Department associate may urgently require further information from the investigator for health authority reporting. Novartis may need to issue an IN to inform all investigators involved in any study with the same study treatment that this SAE has been reported.

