12.3.1 Study drug

The duration of the double-blind treatment will be computed as the time from randomization to the first out of

- a) the last contact to the participant or b) the date of the last diary entry obtained from the participant, what ever comes later
- the participant's death
- or the participant's study completion visit (EOS).

The duration of the on-treatment period will be computed as the time from the first injection to the first out of

- the last injection plus exposure attributable time length of 180 days
- the participant's death
- or the participant's study completion visit (EOS).

This algorithm reflects intended observation period and the planned treatment schedule and the exposure attributable period of the study drug. The duration of the double-blind treatment period and the duration of the on-treatment period will be summarized for the safety set by treatment group descriptively including by duration categories. The overall participant-years of treatment will be computed as the sum of participant years of on-treatment period for all participants.

The number of participants with dose adjustments (interruption or permanent discontinuation) and the reasons will be summarized by treatment and all dosing data will be listed.

The number of study doses administered will also be summarized by treatment group.

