2.7 Safety analyses

All safety parameters will be analyzed based on the SAF, including the secondary safety endpoint.

All listings and tables will be presented by treatment group. Safety summaries (tables, figures) include all data from the double-blind treatment period (i.e. post-baseline assessments) and baseline data.

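### SAEs must be collected until 30 days after the last visit, but the safety tables stop at end of study and no step brings the later events into them

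*Protocol*

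**What the plan says.** **Tables.** Protocol 12.5.3: "Safety summaries (tables, figures) include all data from the double-blind treatment period and baseline data". For adverse events it adds that "summary tables for AEs will summarize all events obtained during double-blind treatment period, with a start date during the double-blind treatment period". On deaths it says only "A separate summary for death will be provided", with no window. SAP 2.7 has "Safety summaries (tables, figures) include all data from the double-blind treatment period (i.e. post-baseline assessments) and baseline data".

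**End of the period.** Protocol 12.3.1 and SAP 2.4.1 both take the earliest of several dates, and the EOS visit is one of them. The on-treatment period uses "the last injection plus exposure attributable time length of 180 days", but EOS is in that list too, so it is also cut there.

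**Collection.** Protocol 10.1.3 requires every SAE, related or not, to be reported until 30 days after the last visit. After EOS the record is made "as paper during the 30 days safety follow-up period after EOS". In Table 8-1 the AE/SAE cell at the follow-up call carries an S. Footnote 7 explains this as source document only, with a paper SAE form sent to safety. Protocol section 8 says that S items "do not need to be recorded in the clinical database", and Protocol 9.3 keeps the information from the call as source documentation.

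**SAP definitions.** SAP 2.7.1 defines a TEAE by onset or worsening after the first blinded injection, with no end date. SAP section 4 bases the AE analysis on TEAEs. SAP 2.7.2 plans a death summary by treatment and a listing of all deaths.

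**The concern.** The trial makes a mandatory call at Day 390 and requires SAE reports up to that point, yet no between-arm table is specified for what it finds. If the Protocol 12.5.3 rule and the capture route are followed as written, SAEs in the follow-up month sit in the safety database and are not compared by arm. The study report and the safety database would then disagree on these events.

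This matters because safety and tolerability are part of the stated purpose (Protocol 1.2), and because Protocol 3.4 itself describes inclisiran as long-acting. The plan attributes 180 days of exposure to an injection, and a participant dosed on Day 270 is well within 180 days of that dose throughout the follow-up month.

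**Working it through.** **Inputs.** Injections on Days 1, 90 and 270 (Protocol 3.4); EOS on Day 360 and the call on Day 390 (Protocol 3.4 and Figure 3-1 notes); attributable length 180 days (Protocol 12.3.1, SAP 2.4.1); 1776 randomized (Amendment 3 rationale).

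**1. The plan's own figure.** EOS + 30 = 360 + 30 = Day 390, which agrees with the stated day of the call.

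**2. Follow-up against the 180-day length.** End = last injection day + 180, first without and then with the cap at EOS.

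| Last injection | Uncapped end | On-treatment end as defined | Days of 361–390 inside uncapped length |
|---|---|---|---|
| Day 1 | 181 | 181 | 0 |
| Day 90 | 270 | 270 | 0 |
| Day 270 | 450 | 360 | 30 |

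The last row applies to any last injection on or after 390 − 180 = Day 210. The first two rows describe participants who stopped injections but stayed in the study to Day 360.

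**3. Observation time not provided for.** 30 / 360 = 8.3%. If all 1776 completed (an assumption), follow-up is 1776 × 30 / 365.25 = 145.9 participant-years, against 1776 × 360 / 365.25 = 1750.5 in the double-blind period.

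**4. Events: illustration only.** The documents give no SAE or death rate. Expected count = 1776 × assumed annual rate × 30 / 365.25, pooled over both arms.

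- SAE rates of 5%, 10% and 20% per year give 7.3, 14.6 and 29.2 events.
- Death rates of 0.5%, 1% and 2% per year give 0.7, 1.5 and 2.9 deaths.

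Each arm would have about half of these if the rates were equal.

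**5. Could the events reach the tables by another route?** Two things would be needed: a rule that admits them and a data source that holds them.

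- Rule: Protocol 12.5.3 excludes AEs that start after EOS. SAP 2.7 repeats the period limit, while the TEAE definition in SAP 2.7.1 sets no end.
- Date handling: SAP 5.1.2 moves an imputed AE date that falls after EOS/EOT back to EOS/EOT. This treats EOS as the outer bound, though only for partial dates.
- Source: follow-up SAEs go to safety on paper and need not be in the clinical database. Neither document describes a transfer or reconciliation into the analysis data.

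**The case against.** A reader might infer that SAEs and deaths after EOS can never appear in any summary. The documents do not go that far, and four objections have force.

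- **The SAP is ambiguous.** Its TEAE definition has no upper limit. SAP 2.7 glosses the double-blind period as post-baseline assessments, and SAP 2.1.1.6 gives those no upper limit either. This stands: the SAP does not clearly exclude the events. It does not supply the data, however, because a definition cannot tabulate records that need not be in the database.
- **Deaths are treated differently.** Neither document gives the death summary its own window, and SAP 2.7.2 lists all deaths. This stands for the listing, provided the deaths reach the database. Exclusion from the summary table rests only on the general sentence in SAP 2.7.
- **The follow-up month is not inside the plan's exposure window.** A reader might infer that it is, from the 180 days. The on-treatment period as defined is cut at EOS, so Day 450 is a date the plan never uses. What remains is narrower: for a last injection on Day 210 or later, the month lies within the attributable length. For those who stopped after Day 1 or Day 90 but stayed in the study, it does not.
- **Stopping the comparison at EOS is defensible.** Planned treatment ends at Day 360 and participants may then receive post-trial access (Protocol 6.1.4, 9.3), so the later month is not a clean continuation of the randomized strategies. This is a good reason to display those events separately, but not to leave them out of every planned table.

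Source-only capture also does not forbid later use of safety-database records. The documents are silent on that, and silence does not show that the sponsor will omit them.

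**Conclusion.** The point holds as a gap in provision. SAE collection runs 30 days past the period that the tables cover, the events are captured outside the clinical database, and neither document says how or whether they enter the SAE tables or the death summary table.

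The size that rests on the documents is 8.3% of the planned double-blind time, or about 146 participant-years on the assumption that all 1776 completed. Event counts depend wholly on assumed rates. The cut-off is the same in both arms, and no between-arm bias is shown.

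The primary endpoint is at Day 90, and the confirmatory muscle-AE and pain endpoints have their own windows ending at Day 360 (SAP 2.6.2.2 to 2.6.2.4), so none of them changes. This is a worthwhile, inexpensive improvement to the safety reporting and does not threaten the main conclusions.

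**What to change.** In Protocol 12.5.3 and SAP 2.7, 2.7.1 and 2.7.2:

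- Keep the double-blind-period tables as planned, including those for non-serious AEs.
- State the cut-off date that applies to TEAEs.
- Add to the SAE and death summaries a separate column for the time from EOS to the end of each participant's safety follow-up.
- Name the data source for that column: safety-database records reconciled with the clinical database.

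The cost is SAP and protocol wording, one data transfer and reconciliation, and an extra column in the SAE and death summaries. Reported SAE and death counts may rise slightly. Some follow-up events may occur under post-trial treatment, so they should stay in their own column and not be pooled with the double-blind period.

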12.5.3.1 Adverse events

All information obtained on AEs will be displayed by treatment group and participant.

The number (and percentage) of participants with TEAEs (events started after the first dose of study medication or events present prior to start of double-blind treatment but increased in severity based on preferred term) will be summarized in the following ways:

- by treatment, primary system organ class and preferred term.
- by treatment, primary system organ class, preferred term and maximum severity.
- by treatment, Standardized MedDRA Query (SMQ) and preferred term.

Separate summaries will be provided for study medication related AEs, death, SAEs, other significant AEs leading to discontinuation

A participant with multiple AEs within a primary system organ class is only counted once towards the total of the primary system organ class.

AEs which will be counted for a specific treatment period are those which are treatment-emergent. These events are those with an onset after the start of the treatment period, or which were present prior to the start of the treatment period but increased in severity, changed from being not suspected to being suspected of study drug relationship, or developed into SAEs after the start of the treatment period.

